8.3. Key Secondary Effectiveness Estimands and Analyses

8.3.1. Key Secondary Effectiveness Estimand 1

The estimand for the key secondary effectiveness endpoint 1 that is defined as a binary variable indicating the subject is alive and has a NLF-SRS response based on the independent blinded photographic reviewers (I, II, and III) assessments of photograph (NLF severity) using the NLF-SRS at Week 24 after initial treatment and relative to baseline assessments. This endpoint will be analyzed as described in [section 8.2](#). Median assessment from three independent blinded photographic reviewers (I, II, and III) will be used for this endpoint assessment.

The analyses performed on FAS will be repeated on PPS population.

8.3.2. Key Secondary Effectiveness Estimand 2

The estimand for the key secondary effectiveness endpoint 2 that is defined as a binary variable indicating the subject is alive and has a NLF-SRS response based on treating investigator live assessments of NLF severity using the NLF-SRS at Week 24 after initial treatment and relative to baseline assessments. This endpoint will be analyzed as described in [section 8.2](#).

The analyses performed on FAS will be repeated on PPS population.

8.4. Sensitivity Analysis

Single imputation:

Best-case analysis will be conducted as sensitivity analysis for the primary outcome measure, as well as the key secondary outcome measures on the FAS and PPS. Missing values will be imputed using single imputation strategy for Princess® FILLER Lidocaine as a response, and for Juvéderm® Ultra XC as a non-response. This endpoint will be analyzed as described in [section 8.2.1](#).

Similarly, worst-case analysis will be conducted as sensitivity analysis for the primary outcome measure, as well as the key secondary outcome measures on the FAS and PPS. Missing values will be imputed using single imputation strategy for Princess® FILLER Lidocaine as a non-response, and for Juvéderm® Ultra XC as a response. This endpoint will be analyzed as described in [section 8.2.1](#).

Multiple imputation:

A sensitivity analysis will be conducted for the estimand of the primary outcome measure, as well as the key secondary outcome measures (NFL-SRS assessments) using a method of multiple imputation on the FAS and PPS, under the missing-at-random (MAR) assumption for all missing values at Week 24. If baseline is missing one side of the face, then impute from the other side of the face, but if baseline is missing for both sides of the face then impute using multiple imputation with the Markov Chain Monte Carlo (MCMC) method. Additionally, a tipping point analysis will be performed for the estimand of the primary outcome measure, as well as the key secondary outcome measures on the FAS, by performing a series of multiple imputations with adding an increasing shift value to the original NLF-SRS scale (discrete) of imputed subjects prior to performing the treatment comparison to investigate the impact of the deviation from MAR assumption. The number of completed datasets for each multiple imputation approach will be 100. The multiple imputations will be performed via SAS PROC MI procedure.

Impute: The missing values on the NLF-SRS scale (discrete) will be multiple imputed (using MAR assumptions) for each subject (with missing NLF-SRS post-baseline) with a set of 100 plausible values, thus 100 completed datasets will be produced. The multiple imputations will be done via SAS PROC MI. As per MAR assumption, all available observations with similar baseline characteristics from same treatment group are used to derive the imputation model.

This document is confidential.

The following statements use the MI procedure to impute missing values under the MAR assumption:

Achieve monotone missing data pattern for all visits:

```
proc mi data=dain seed=12345 nimpute=100 round=1 minimum=0 maximum=4
out=mono;
  class treatment;
  var treatment sex age base week12 week24;
  mcmc impute=monotone;
run;
```

Impute under the MAR assumption for all visits with monotone missing data pattern:

```
proc mi data=mono seed=12345 nimpute=1 round=1 minimum=0 maximum=4
out=outmi;
  by _Imputation_;
  class treatment;
  var treatment sex age base week12 week24;
  monotone reg;
run;
```

Categorization of Response: The category of response/non-response for each subject will be derived based on the imputed NLF-SRS scale for the missings in each of the 100 completed datasets.

Analyze: The analysis method as described in [section 8.2.1](#) will run in each of the 100 completed datasets using binary response data.

Combine: The analysis results / estimates resulting from 100 completed datasets will be combined using Rubin's combination rules (Rubin D.B., 2004) with SAS MIANALYZE procedure.

```
ods output parameterestimates=paramest;
proc mianalyze data=paramest;
  modeleffects estimate;
  STDERR stderr;
run;
```

Tipping point is a series of multiple imputations whereby a shift (here a positive shift) will be applied on the original NLF-SRS scale (discrete) of imputed subjects to the treatment group Princess® FILLER Lidocaine, which results then in the decrease of the number of responses in this group, and thus decreases the likelihood of non-inferiority against the control treatment Juvéderm® Ultra XC. This shift is only applied to subjects where missing values have been multiple imputed.

The positive shift of 1, 2, 3, 4 will be performed in each step, until the point is reached where the statistically significant non-inferiority switches to statistically non-significant: This respective shift where this happens is the tipping point.

A sample of SAS code for sensitivity analysis using the tipping-point method could refer to:

```
/*-----*/
/*--- Performs multiple imputation analysis           ---*/
/*--- for specified shift parameters:                 ---*/
/*--- data= input data set                           ---*/
```

This document is confidential.

```
/*--- smin= min shift parameter ---*/
/*--- smax= max shift parameter ---*/
/*--- sinc= increment of the shift parameter ---*/
/*--- outparams= output reg parameters ---*/
/*-----*/

%macro miparams(data=, smin=, smax=, sinc=, outparams=);
ods select none;

data &outparams;
  set _null_;
run;

/*----- # of shift values -----*/

%let ncase= %sysevalf( (&smax-&smin)/&sinc, ceil);

/*---- Multiple imputation analysis for each shift ----*/
%do j=0 %to &ncase;
  %let sj= %sysevalf( &smin + &j * &sinc);

/*---- Generates 100 imputed data sets ----*/

proc mi data=&data seed=12345 nimpute=100 round=1 minimum=0 maximum=4
out=mono;
  class treatment;
  var treatment sex age base week12 week24;
  mcmc impute=monotone;
run;

proc mi data=mono seed=12345 nimpute=1 round=1 minimum=0 maximum=4 out=outmi;
  by _Imputation;
  class treatment;
  var treatment sex age base week12 week24;
  monotone reg;
  mmar adjust( week24 / shift=&sj adjustobs=(treatment='1') );
run;

/*---- Categorization of response in imputed data sets ----*/

data outmi;
  set outmi;
  chg= week24 - base;
  if chg<0 then response=1;
  else response=0;
run;

/*----- Perform genmod test -----*/

ods output parameterestimates=paramest;
proc genmod data=outmi;
```

This document is confidential.

```
    by _Imputation_;
    class id treatment;
    model response (event='1')=treatment/dist=binomial link=identity;
    repeated subject=id;
    lsmeans treatment/diff cl;
    lsmestimate treatment/cl lower testvalue=-0.1 alpha=0.025;
run;

/*----- Combine genmod results -----*/

ods output parameterestimates=miparams;
proc mianalyze data=paramest;
    modeleffects estimate;
    STDERR stderr;
run;

data miparams;
    set miparams;
    Shift= &sj;
    keep Shift Probt;
run;

/*----- Output multiple imputation results -----*/
data &outparams;
    set &outparams miparams;
run;

%end;

ods select all;
%mend miparams;
```

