6.3. Missing Data

For safety analysis missing data will not be estimated and/or imputed in any way. All subjects who withdraw prematurely from the study will be documented and the reason for withdrawal will be reported in the Clinical investigation report. All available data from subjects who withdraw will be listed and all available planned data will be included in the summaries according to analysis data sets.

In case of an AE/ ADE with partial/ missing start/ stop dates, the rules outlined in Section 9.3 will be applied.

Subjects with missing NLF-SRS grades at Baseline and/or at Week 24 will be considered as non-responders for the primary analysis. Since it is very unlikely that the assessment of only one NLF will be missing, presumably either no or both assessments will be available for one subject at a certain time point. Therefore, this imputation method will probably decrease the response rate in both treatment groups simultaneously. Due to the fact that the sample size calculation was based on rather high response rates (88% for Juvéderm® Ultra XC and 87% for Princess® FILLER Lidocaine), lower response rates will make it more difficult to demonstrate non-inferiority of Princess® FILLER Lidocaine and thus this approach is considered to be conservative. In addition to this approach, a complete case analysis (using the available data without any imputation), a best-case analysis (missing values for Princess® FILLER Lidocaine will be considered as a response, missing values for Juvéderm® Ultra XC will be considered as a non-response), a worst-case analysis (missing values for Princess® FILLER Lidocaine will be considered as a non-response, missing values for Juvéderm® Ultra XC will be considered as a response), and a tipping point analysis will be conducted as sensitivity analyses.

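### Multiple imputation draws the two folds of a face without reference to each other, so the sensitivity intervals for the paired difference come out slightly too wide

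*SAP*

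**What the plan says.** SAP 8.4 plans multiple imputation of missing Week 24 NLF-SRS grades under missing-at-random, for the primary and both key secondary endpoints, on the FAS and PPS. A tipping-point version follows on the FAS. Every PROC MI call uses the list "var treatment sex age base week12 week24": one baseline, one Week 12 and one Week 24 grade per record. The text agrees with the code: "all available observations with similar baseline characteristics from same treatment group are used to derive the imputation model".

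The records are single folds. Every subject receives both devices, the completed data go straight into a GENMOD step with "class id treatment", and the tipping-point shift is restricted by "adjustobs=(treatment='1". The one stated use of the contralateral fold concerns baseline: "If baseline is missing one side of the face, then impute from the other side of the face".

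After imputation the analysis clusters on the subject through "repeated subject=id", and Rubin's rules combine the results. On the number of imputations: "The number of completed datasets for each multiple imputation approach will be 100". On the expected pattern of missing data, SAP 6.3 says "presumably either no or both assessments will be available for one subject at a certain time point". SAP 2.7 expects agreement between the two folds of a face, and SAP 8.2.1 compares paired proportions.

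**The concern.** The analysis model relies on the dependence between the two folds of a face, and the imputation model leaves it out. When both Week 24 grades are missing, the two values are drawn independently given treatment, sex, age and each fold's own earlier grades. If folds agree more than those covariates explain, the imputed faces are too often discordant, and discordance drives the variance of a paired difference.

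What is at stake is how the robustness analyses read. Limits that are too wide can make the result look more fragile than it is, and could bring the tipping point at a smaller shift than it should. The other fold's Week 12 grade, where observed, also goes unused as a predictor.

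**Working it through.** **Inputs from the documents.** Response rates 87% and 88%, with a discordant proportion of 21.9% under independence (SAP 2.7); 270 randomized (SAP 2.6); loss to follow-up about 5% (protocol 9.3); margin -10% and a two-sided 95% interval (SAP 8.2.1).

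**Assumed, not in the documents.** The correlation phi between the two folds' responses (the SAP gives only its sign), the baseline mix of grades 2 and 3, and the correlation between visits.

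**1. The plan's own figures.** Discordance under independence is 0.87 × 0.12 + 0.88 × 0.13 = 0.2188, which matches 21.9%. With these inputs, 222 subjects and the one-sided 95% Newcombe limit, simulated power is 88.6% against the stated 90%, so the inputs are read correctly.

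**2. Closed form, within-imputation variance only.** For one face:
- Independent folds: Vi = 0.87 × 0.13 + 0.88 × 0.12 = 0.2187.
- Correlated folds: Vc = Vi − 2 phi √(0.1131 × 0.1056) = 0.2187 − 0.2186 phi.
- SE ratio when a fraction f of faces is drawn independently: √[((1 − f)Vc + f Vi)/Vc].

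At phi = 0.5, Vc = 0.1094 and Vi/Vc = 2.00. The ratio is √1.05 = 1.025 at f = 5% and √1.10 = 1.049 at f = 10%. At phi = 0.3 it is 1.011 and 1.021; at phi = 0.7, 1.057 and 1.110; at phi = 0, exactly 1. This formula assumes full independence, ignoring dependence carried by shared covariates, and it omits between-imputation variance. It is only a guide.

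**3. Simulation of the whole procedure.** There were 270 faces and 700 trials per setting, with both devices at about 87.6% response. Both folds were missing together at Week 24, and half of those faces also lacked Week 12. Thirty imputations were used instead of 100 for speed. Fold-level imputation as in the SAP was compared with one-row-per-face imputation; both used the subject-clustered variance and Rubin's rules. Mean pooled SE:

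| phi | Missing | SAP code | One row per face | Excess |
|---|---|---|---|---|
| 0 | 5% | 0.0293 | 0.0293 | none |
| 0 | 10% | 0.0301 | 0.0302 | none |
| 0.26 | 5% | 0.0256 | 0.0252 | 1.6% |
| 0.26 | 10% | 0.0267 | 0.0260 | 2.7% |
| 0.26 | 20% | 0.0291 | 0.0279 | 4.3% |
| 0.52 | 5% | 0.0212 | 0.0203 | 4.4% |
| 0.52 | 10% | 0.0228 | 0.0210 | 8.6% |
| 0.52 | 20% | 0.0260 | 0.0228 | 14.0% |

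**4. Mechanism.** Under the SAP code 24-25% of imputed faces are discordant at every phi. The complete data have about 16% (phi 0.26) and 10% (phi 0.52); one row per face gives about 20% and 14%.

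**5. Direction.** At the two positive correlations, pooled SE divided by the actual SD of the estimate is about 1.06 (5% missing) and 1.10-1.18 (10%) under the SAP code, against 0.99-1.03 with one row per face. Each SD carries Monte Carlo error of about 1/√1400 = 2.7%. Over all settings, the mean estimate under the SAP code stays within 0.0022 of zero, where the true difference was set, and its nominal 95% interval covers 95-99%.

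**6. On the scale of the margin.** At 5% missing the lower limit moves by 1.96 × 0.0004 = 0.08 points (phi 0.26) or 1.96 × 0.0009 = 0.18 points (phi 0.52), against a 10-point margin. The share of trials meeting the margin was 98.4% under both methods at phi 0.26, and 99.6% against 99.7% at phi 0.52.

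**The case against.** A reader might infer that the pairing is thrown away altogether. It is not: every completed data set is analysed with clustering on the subject, so all faces with observed grades keep their pairing. Only faces missing Week 24 are affected.

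A reader might also picture the imputed folds as belonging to two unrelated people. That goes too far. The two folds share sex and age, eligibility requires the same severity on both sides (SAP 2.6.1), and each fold's Week 12 grade carries within-face information where it was observed. The draws are independent only conditionally on these.

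Other points on that side stand:
- The 10% figure in SAP 2.6 combines drop-out with major protocol deviations, and SAP 5.1 uses deviators' Week 24 grades. It is not a Week 24 missingness rate; about 5% is the better planning value.
- Not all the excess discordance comes from lost pairing. Some remains with one row per face, and a similar excess appears when the folds are truly independent.
- With both folds expected to be missing together, a contralateral Week 24 grade would rarely be available. The unused information is mainly contralateral Week 12.
- No changed conclusion has been shown. The tipping-point analysis was not itself simulated, and its whole-grade shifts may not move with so small a change in standard error.

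That the code is illustrative is a weaker defence. The tipping-point macro is labelled a sample, but the missing-at-random statements are presented as the procedure itself, and the text describes no joint model for the two folds.

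**Conclusion.** The point holds in limited form. As written, the multiple imputation and tipping-point analyses overstate the standard error of the paired difference, by about 2-4% at 5% missing and 3-9% at 10%, if the fold correlation lies between about 0.26 and 0.52. With independent folds there is no excess at 5-10% missing. The correlation is an assumption, so the sizes depend on it and on the other simulation settings.

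A reader might infer that wrong error bars threaten the non-inferiority claim. The documents do not support that. The intervals err on the wide side, the estimate is essentially unbiased, and these are sensitivity analyses outside the six-step testing hierarchy in SAP 8. The primary analysis counts missing grades as non-response and does not use this model. The practical consequence is a robustness check slightly more pessimistic than it need be, with a tipping point that may come early. The change is worth making because it is cheap, but it is an optional refinement.

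**What to change.** Impute with one row per subject. The variables are sex, age, baseline, and the Week 12 and Week 24 grades of both the Princess fold and the Juvéderm fold. Enter a single common baseline where eligibility makes the two folds' grades identical, because entering both would be collinear. Enter both baselines where they can differ, as in the photographic ratings.

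For the tipping point, apply the shift to the Princess Week 24 variable in place of the restriction by treatment code, and drop treatment from the CLASS and VAR statements of PROC MI. Then derive response for each fold, reshape to one record per fold, and run the GENMOD and MIANALYZE steps already planned. State in the text of SAP 8.4 that the two folds are imputed jointly.

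The cost is a modest amount of reprogramming: a transpose, a new variable list, a rewritten shift statement and a reshape back. No data collection or primary analysis changes.

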2.6.1. Inclusion Criteria

Subjects who meet **ALL** the following criteria are eligible for this clinical investigation:

1. Male or female subjects aged ≥ 22 years at Screening Visit
2. Subjects with two fully visible, approximately symmetrical moderate to severe nasolabial folds (same severity) with severity scores of 2 or 3 (moderate or severe) on the 5-point NLF-SRS for both NLFs as judged by the treating investigator in conjunction with the independent blinded evaluating investigator
3. Females of childbearing potential must have a negative urine pregnancy test at injection visits and must agree to use an adequate method of contraception for the duration of the clinical investigation
4. Healthy skin in the nasolabial area and free of diseases that could interfere in cutaneous aging evaluation and/or injection
5. Willingness to abstain from any aesthetic or surgical procedures in the treatment area for the duration of the clinical investigation, including botulinum toxin injections (except glabella or forehead botulinum toxin treatment)
6. Subjects having understood the purpose and conduct of the clinical investigation, having given written informed consent, and are willing and able to adhere to the Clinical Investigation Plan (CIP)

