6.2. Key Definitions

The study day is the day relative to the date of first administration of Investigational Medical Device (IMD), where Day 1 is the day of first administration of IMD.

The first dose date is defined as the first non-missing date where an administration of IMD was recorded. The last dose date is defined as the last non-missing date where an administration of IMD was recorded.

For on-treatment events (on or after first dosing day), Study Day = Event Date - date of first administration of IMD + 1; and for pre-treatment events (prior to first dosing day), Study Day = Event Date - administration of IMD.

Unless otherwise specified, baseline is the last non-missing observation before the administration of IMD, which is expected to be Day 1, or Screening if the Day 1 data are not available.

This document is confidential.

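### The whole-grade tipping-point grid in SAP 8.4 is too coarse to show how far the imputed Princess response rate must fall before non-inferiority is lost

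*SAP*

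**What the plan says.** SAP 8.4 plans a tipping-point analysis on the FAS for the primary and both key secondary endpoints. Missing Week 24 grades are multiply imputed under missing-at-random, and a positive shift is then added on the Princess side: "The positive shift of 1, 2, 3, 4 will be performed in each step, until the point is reached" at which significance is lost. The result is defined by the shift itself: "This respective shift where this happens is the tipping point". Observed values are left alone: "This shift is only applied to subjects where missing values have been multiple imputed".

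Three other details matter:

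- Imputed grades are whole numbers from 0 to 4 ("proc mi data=dain seed=12345 nimpute=100 round=1 minimum=0 maximum=4").
- Any drop from baseline is a response ("if chg<0 then response=1").
- Eligibility under SAP 2.6.1 requires "severity scores of 2 or 3 (moderate or severe) on the 5-point NLF-SRS for both NLFs", as judged live by the investigators.

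The sample macro leaves the step size open ("sinc= increment of the shift parameter"), but the text fixes whole grades.

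**The concern.** A tipping-point analysis should tell the reader how unfavourable the missing outcomes must be before the conclusion fails, so that the plausibility of that assumption can be judged. The best-case and worst-case analyses already supply the extremes. What this analysis can add lies between them.

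One grade is both the step of the grid and the response threshold. The first step therefore moves the imputed Princess response rate a long way, and the grid barely samples the region of interest. The reported shift is also not a response rate, and the sample macro keeps only the shift and its p-value. A reader who is told the tipping point is shift 1 cannot tell from that whether the conclusion needs a modest or a severe drop in response among the missing.

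**Working it through.** **Inputs.** From SAP 2.7: response 87% (Princess) and 88% (Juvéderm), folds independent. From SAP 2.6: about 270 randomized. From SAP 8.2.1: margin -10%, one-sided 0.025. From Protocol 9.3: about 5% lost to follow-up, and 0.05 × 270 = 13.5, so 14 subjects. The documents give no distribution of grade improvement, so that part is assumed and varied.

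**The plan's own figure.** A simulation with these rates and the Newcombe-Wilson interval at one-sided 0.05 (the level in SAP 2.7) gives 88.6% power at 222 subjects, against 90% stated. The inputs are close enough to use.

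**Step 1: what each shift does.** A fold responds if (Week 24 grade + shift) < baseline. With baseline 2 or 3 and Week 24 at least 0, improvement is at most 3 grades. Shift 1 removes all imputed one-grade responders, shift 2 all two-grade responders, and shift 3 the rest. Shift 4 then changes nothing. With baseline 4, a 4-to-0 change is still a response at shift 3 but not at shift 4.

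**Step 2: size of the steps.** Assume improvement is normal with mean 1.3 and SD 0.75, rounded to whole grades.

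- Shift 0: P(improvement > 0.5) = Φ(0.8/0.75) = 86%
- Shift 1: P(improvement > 1.5) = Φ(-0.2/0.75) = 39%
- Shift 2: 0% for baseline 2 and Φ(-1.2/0.75) = 5% for baseline 3, about 3% for an even split
- Shift 3: 0%

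Other assumed mean/SD pairs give a first step of 80% to 20% (1.0/0.6), 79% to 42% (1.3/1.0) and 93% to 55% (1.6/0.75).

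**Step 3: the breaking response rate.** Among observed pairs, Princess-only response is 0.87 × 0.12 = 0.1044 and Juvéderm-only is 0.13 × 0.88 = 0.1144. Let f = m/270 be the missing share and r the Princess response rate among the missing, with imputed Juvéderm at 88%:

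- a = (1 - f) × 0.1044 + f × r × 0.12
- b = (1 - f) × 0.1144 + f × (1 - r) × 0.88
- d = a - b
- lower limit L = d - 1.96 × √[(a + b - d²)/270]

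Example with m = 14, r = 0.39: f = 0.0519, a = 0.1014, b = 0.1363, d = -0.0349, L = -9.3%. At r = 0.03, d = -0.0536 and L = -11.3%. Solving L = -10% for r gives the breaking rate.

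| Missing | L at 87% | L at 39% | L at 3% | Breaking rate | Grid reports |
|---|---|---|---|---|---|
| 14 | -6.6% | -9.3% | -11.3% | 26% | 2 |
| 20 | -6.6% | -10.4% | -13.3% | 45% | 1 |
| 27 | -6.6% | -11.8% | -15.6% | 56% | 1 |

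At r = 0, L is -9.7% with 9 missing and -10.1% with 10. Below about 10 missing, no Princess-only shift tips the result on any grid.

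**Step 4: the label depends on the distribution, the breaking rate does not.** With 14 missing the breaking rate is 26%. The grid reports 2 if shift 1 leaves 39%, but 1 if shift 1 leaves 20%. With 27 missing, a responder mix of 25/50/12 (per cent with one, two and three grades) leaves 62% at shift 1, so the grid reports 2 rather than 1.

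The calculation uses expected counts and ignores between-imputation variance.

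**The case against.** The strongest reply is that the grid works. A reader might infer that it cannot locate a tipping point at all. That is not so: it brackets the tip to one grade, and for live ratings it ends with every imputed Princess fold a non-responder, so finding no tip is also informative. A whole grade is the unit of the scale and of the responder definition.

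A reader might also infer that the grid confuses a break at 80% response with one at 40%. At the planned rates a break at 80% needs about 122 of 270 missing (45%), far above the expected 5%. It becomes relevant at 14 to 27 missing only if the observed difference is already near -4%.

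Other planned output helps as well. The macro keeps a p-value at every shift, and best-case, worst-case, complete-case and missing-at-random analyses are planned. The table shells are a separate document and may show response rates by shift. The sizes in Step 2 rest on assumed distributions.

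Finally, the claim that shift 4 always repeats shift 3 goes too far. The limit of 3 comes from live eligibility. It does not bind the median photographic rating used for key secondary endpoint 1, and it is not guaranteed for a pre-treatment Visit 2 rating if that serves as baseline under SAP 6.2 ("baseline is the last non-missing observation before the administration of IMD, which is expected to be Day 1"). If truncation at 0 follows the shift, shifts 3 and 4 could also differ slightly (about 0.1 point, assumed SD 0.7). Where shift 4 is redundant it is harmless.

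All of this stands. It does not remove the coarseness of the first step, which appears under every distribution tried, or the lack of a planned breaking response rate in the SAP text.

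**Conclusion.** The grid locates the tipping point only to a whole grade, and that is too coarse to show how far Princess response among the missing must fall. The first step drops it by 37 to 60 percentage points under the four normal distributions tried. Breaking rates of about 26%, 45% and 56% (14, 20 and 27 missing) are reported as shift 2, 1 and 1 under the 1.3/0.75 distribution. These rates assume the planned 87% and 88%, independent folds, imputed Juvéderm at 88%, n = 270 and one-sided 0.025. Replacing 1.96 by 1.645 (one-sided 0.05) lowers them to about 9%, 33% and 47%.

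This is a sensitivity analysis, so no confirmatory decision changes. The documents do not support saying that the grid fails to find a tipping point, or that shift 4 is useless for all three endpoints. The weakness is limited resolution in the one region this analysis is meant to explore, and it does not arise if fewer than about 10 subjects are missing.

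**What to change.** Replace or supplement the shift grid in SAP 8.4 with a grid on counts. For the m FAS subjects without a Week 24 grade, vary the number of imputed responders from 0 to m for each filler, mark where the lower limit is -10% or below, and report the Princess response rate among the missing at that boundary. In the 14-missing example, with Juvéderm at 88%, 4 Princess responders (29%) keep non-inferiority and 3 (21%) lose it.

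If the multiple-imputation shift is kept:

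- State that rounding follows the shift. The SAP does not say; if rounding comes first, shifts below 1 change nothing.
- Use steps of at most 0.25 grade. Under the 1.3/0.75 assumption these give 77%, 66%, 53% and 39% up to a shift of 1.
- Report the imputed response rate at each shift.
- Keep shift 4 for the photographic endpoint.

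The cost is a few lines of SAP text and a small amount of extra programming.
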